- *Motor impairments*: including tremor, decreased range of movement, muscle weakness, and/or having the affected limb set in a sustained, fixed posture (i.e. dystonia)⁶.

Sensorimotor interventions (i.e. interventions aiming to improve sensory and motor feedback of the affected limb) have shown promising outcomes on increasing perception associated with the affected limb (i.e. tactile acuity; precision with which we can sense touch⁸) and decreasing pain intensity^{9,10,11}. Although its mechanisms are largely unknown, it is thought that the 'normalized' sensory and motor feedback may compete with pain stimulus resulting in pain reduction in people with CRPS^{9,12}. The evidence for the effectiveness of these treatment modalities in CRPS is weak, and often focus only on pain reduction. Thus further research is required on novel sensorimotor interventions that target also other abnormalities present in CRPS (i.e. body perception disturbances, loss of self-ownership and amputation desire and motor impairments)¹³.

Cognitive Multisensory Rehabilitation¹⁴⁻¹⁹ is a term agreed by the International Cognitive Multisensory Rehabilitation Centre to describe a sensorimotor intervention originally developed for stroke motor rehabilitation by [name] (1940-2020). CMR targets somatosensory and multisensory and cognitive functions through sensory discrimination exercises¹⁻³. It focuses on the perception and integration of different sensory modalities (e.g. somatosensory, visual, etc.) and body parts (e.g. shoulder and hand) in order to produce purposeful, effective and accurate movements allowing an appropriate relationship with the surrounding environment.

Clinical observations from the CRPS service at the Royal United Hospital (RUH) have suggested that CMR may have an impact on symptom reduction (e.g. decreased body perception disturbances or pain reduction) as a part of a multidisciplinary rehabilitation programme.

In contrast to other sensorimotor interventions, CMR offers a comprehensive range of sensorimotor tasks targeting a wider range of sensorimotor, cognitive and body representation impaired functions in CRPS (i.e. body perception disturbances, loss of self-ownership and amputation desire, allodynia and motor impairments). In CMR, patients are guided to increase their affected limb's perception by discriminating different sensory information through the activation of cognitive processes (such as perception, attention or body representation) and mindful movements (See *figure 1*).

[figure not shown]

Figure 1: Cognitive Multisensory Rehabilitation components

Furthermore, unlike sensorimotor interventions, CMR tasks are considered to be discrimination-based: e.g. the patient has to recognise different types of stimuli on the painful limb, such as which fabric they feel (i.e. tactile discrimination). Because of

this, CMR interventions require a trained facilitator whose role is to help the patients to recognise the different sensory information with eyes closed by physically guiding the patient as well as posing the cognitive question. Preliminary data¹⁰ has shown that improvements in pain levels observed following sensorimotor interventions were enhanced and lasted longer if people with CRPS discriminated between different stimuli as opposed to just receiving sensory stimulation on the painful body part. This suggested that a broader activation of cognitive processes such as problem solving, attention and perception may increase the effectiveness of sensorimotor interventions.

Recently, Covid-19 restrictions have prompted the increase of home-based treatment complementing therapy treatment. Home-based discrimination sensory retraining has shown promising results in pain reduction for people with CRPS¹¹.

Overarching hypothesis

Is CMR a treatment that can be adapted to treat CRPS patients in a home-based environment by a trained treatment partner?

Research questions to be answered

1. Is CMR a suitable, feasible, efficient and safe treatment intervention to treat people with CRPS in a home-based environment by a trained treatment partner?

Aims of the study

1. To identify relevant information regarding the delivery of CMR in CRPS patients in a home-based environment by a trained treatment partner, in terms of:
 - a. Suitability: to determine if the intervention is appropriate for CRPS patients.
 - b. Feasibility: to determine the degree to which the intervention can be easily and safely delivered by a trained treatment partner and received by a CRPS patient.

Design

A feasibility study design will be used to address the aims of this research.

Study population

CRPS patients who access the CRPS Service at the Royal United Hospital in Bath and their treatment partner (i.e. participants' relative or friend).

Study sample

A total sample of ten participants will be recruited for the study: five people with CRPS who access the CRPS Service at the Royal United Hospital and their treatment-partner (i.e. participants' husband, wife, friend, etc.). This sample is considered sufficient for this type of study to obtain enough data to meet the identified aims of this study.

Description of study population

Recruitment selection criteria

1) CRPS patients from the CRPS Service at the Royal United Hospital.

Inclusion criteria:

- Participants meet the Budapest criteria for Type I CRPS⁴ (i.e. the diagnostic criteria for CRPS) in one limb (unilateral).
- Pain duration for a minimum of 3 months.
- 18 years in age or older.
- Able to understand verbal and written English.
- Willing to participate and provide written informed consent.
- Have someone available to act as treatment facilitator and consent to participate in the study.

Exclusion criteria:

- Presence of any co-morbidity that may influence CRPS symptoms including stroke, diabetic peripheral neuropathy, progressive neurological disease such as multiple sclerosis, and Parkinson's disease.
- Presence of Post-Traumatic Stress Disorder or other psychological conditions hindering patients' ability to engage with the intervention.
- Serious ill health.

2) Treatment partner

Inclusion criteria:

- 18 years in age or older.
- Able to understand verbal and written English.
- Willing to participate and provide written informed consent.
- Able to commit to delivering the treatment with the patient regularly within the home environment.

Exclusion criteria:

- Serious ill health.
- Inability to deliver the treatment due to time, physical, mental or other constraints.

3. Research procedures

3.1 Recruitment including informed consent

a) CRPS potential participants will be recruited via the following ways:

- i. In the initial assessment at the CRPS Service in the RUH by the clinical multi-disciplinary team. Potential recruits will be approached by a member of the CRPS multidisciplinary team (independent from the research lead) during the initial assessment. If they are interested in participating, a recruitment pack will be handed to them.
- ii. In a planned admission of patients to the CRPS residential programme. Prior to the admission in the CRPS residential programme, the CRPS administration team will send out the recruitment pack to all CRPS patients.

The recruitment pack will contain an invitation letter, participant information sheet, reply slip and freepost envelope. Alternatively, these documents can be provided electronically (i.e. by email). The recruitment pack will contain the contact details for the lead investigator.

In order to ensure those CRPS patients that have already been approached and not responded at the initial assessment are not then approached for the second time if booked on the programme, CRPS administration will keep a log of packs handed

(see appendix 4). Some patient planned admission are CRPS patients returning to the CRPS inpatient program and therefore do not go through the initial assessment route.

b) Treatment partner will be identified by the CRPS patients among friends and relatives. Once CRPS potential participants will have shown interest in participating in the study, they will be asked to provide us with the contact details of a potentially interested friend or relative. A separate recruitment pack containing will be sent to them with an invitation letter, participant information sheet, reply slip and freepost envelope and/or will provide these documents electronically (i.e. by email).

Expressions of interest in study

Having read the participant information sheet, if the CRPS potential participant is interested in the study and identifies a potential treatment partner, they will contact [name] via face-to-face/phone/reply slip or email. [name] then will contact the potential CRPS patient and treatment partner. Both CRPS patients and treatment-partner will have the opportunity to discuss any remaining queries/concerns as well as explore practical and technical issues regarding their participation in the study (e.g. total amount of practice during the intervention period, the frequency of the session and the time for the intervention to be delivered). [name] will confirm that they meet the eligibility criteria for the study.

[figure not shown]
Eligibility, screening and consent

CRPS participants and treatment partner that meet the eligibility criteria will be given a consent form (either in a physical document or in electronic format, (see form in appendix 3)).

Once CRPS patients and treatment partner have given informed consent to take part in the study, they will agree with [name] on the date and time for all the sessions (Session 1, Intervention phase and Session 2) and make an appointment date for Session 1. Four copies of the signed consent form for CRPS patients and treatment partner will be made, one for the CRPS patient another for the treatment partner (to keep), one filed in the medical notes (if they are a patient at the CRPS Service) and digitally scanned and the other kept in the research site file on a password protected digital folder.

3.3 Methods

The outline of study sessions is presented in figure 2:

Session 1: Pre-intervention clinical assessment and Intervention Training

Session 1 will take place in a confidential clinic room at the RUH and will comprise two parts: pre-intervention clinical assessments and intervention training for treatment partner.

- **Baseline clinical assessment (Outcome measures)**

CRPS participants will be asked to fill in patient-reported outcome measures (PROMS) as follows:

Pain (Neuropathic Pain Symptom Inventory²⁰ and Numerical Rating Scale²¹); Pain interference (Neuropathic Pain Symptom Inventory²⁰);

*Neuropathic Pain Symptom Inventory*²⁰: The Neuropathic Pain Symptom Inventory (NPSI) is one of the most widely used tools for characterizing neuropathic pain symptom severity. The NPSI is comprised of five subscales, each representing different dimensions of neuropathic pain: burning spontaneous pain (burning), pressing spontaneous pain (pressing), paroxysmal pain (paroxysmal), evoked pain (evoked), and paraesthesia/dysesthesia. Moreover, the NPSI has good construct validity, high test-retest reliability, and good sensitivity to change in people with peripherally mediated neuropathic pain.

*Numerical Rating Scale*²¹: The Numerical Rating Scale (NPRS-11) is an 11-point scale for self-report of pain. It is the most commonly used unidimensional pain scale. The respondent selects a whole number (integers 0–10) that best reflects the

intensity (or other quality if requested of his/her pain. The anchors are 0 = no pain and 10 = extreme pain/worst possible pain (there are various different wordings of the upper anchor). It is often categorised into: no pain = 0, mild pain= 1-3, moderate pain = 4-6, severe pain = 7-10. Moreover NPRS has shown to be highly correlated with the Visual Analogue Scale (VAS), ranging from 0.86 to 0.95 and has a high test-retest reliability ($r = 0.95$)²²

*Chronic Pain Acceptance Questionnaire (CPAQ-revised)*²³. The 20-item CPAQ-revised has been designed to measure acceptance of pain. The acceptance of chronic pain is thought to reduce unsuccessful attempts to avoid or control pain and thus focus on engaging in valued activities and pursuing meaningful goals. There have been 2 factors identified in the CPAQ-Revised: (1) Activity engagement (pursuit of life activities) (2) Pain willingness (recognition that avoidance and control are often unworkable methods of adapting to chronic pain). The items on the CPAQ are rated on a 7-point scale from 0 (never true) to 6 (always true). To score the CPAQ, items for Activity engagement and Pain willingness to obtain a score for each factor. To obtain the total score, add the scores for each factor together. Higher scores indicate higher levels of acceptance. CPAQ-revised has shown very good to excellent internal consistency with alphas of .82 (Activity engagement) and .78 (Pain willingness) and moderate to high correlations with measures of avoidance, distress, and daily functioning.

Kinesiophobia

*Tampa Scale of Kinesiophobia*²⁴: The Tampa Scale for Kinesiophobia (TSK) is a 17 item questionnaire used to assess the subjective rating of kinesiophobia or fear of movement. The TSK is a self-completed questionnaire and the range of scores are from 17 to 68 where the higher scores indicate an increasing degree of kinesiophobia. The questionnaire using 4 points to assess that are based on; the model of fear-avoidance, fear of work-related activities, fear of movement, and fear of re-injury²⁵. Several studies have found the scale to be a valid and reliable psychometric measure²⁶.

Body perception disturbance of painful limb:

The Bath CRPS body perception disturbance scale is used to measure changes in body perception of the affected limb⁷. Values of 0.66 for Cronbach's alpha and 0.87

for Cohen's kappa suggest adequate internal consistency^{27,28} and adequate interrater reliability²⁹ of the scale.

In order to obtain the nature and extent of these perceptual disturbances the questionnaire comprises seven items covering different aspects related to the affected limb. These are: (1) a sense of ownership; (2) limb position awareness; (3) attention paid to the limb; (4) emotional feelings towards the limb; (5) perceptual disparities in size, temperature, pressure and weight (compared to the unaffected limb); (6) a desire to amputate the limb; and (7) a mental representation of the affected limb.

Five of these seven items are rated on a 0 to 10 scale to establish the extent of abnormality within that item. The sixth item determines the subjective perception of changes in size, weight pressure and temperature. The final item illustrates the mental representation of both the affected and unaffected limbs. The final item involves an illustration of the mental representation of both the affected and unaffected limb. With eyes closed the participant generates a mental picture of both upper limbs commencing with their unaffected side. As the participant verbalises their mental image the assessor draws a picture of both limbs based on these descriptions. The resultant drawing is assessed by the participant for accuracy and truthfulness and adjusted as necessary by the experimenter following the participant's instructions. The drawing is independently graded by the experimenter on a three-point scale: no distortion=0, distortion=1, severe distortion=2. If either a distortion in size or shape is depicted within the drawing, or the accompanying textual descriptions, i.e. that it is not anatomically consistent with the actual size or shape of the limb, the rating 'distortion' is given by the experimenter. A rating of 'severe distortion' is given if one or more segments of the limb are missing. The total score is calculated by summing the individual scores of the seven items⁷. The higher the score the greater is the degree of disturbance. Estimated completion time is 5 minutes. Patients' body perception disturbances will be assessed using this tool twice in total – once at the beginning of session 2 and once at the end of session 3.

Physical function PROMIS-29 v2.0 profile³⁰

Evaluation of Daily Activity Questionnaire³¹: The Evaluation of Daily Activity Questionnaire (EDAQ) is a self-report assessment. It evaluates, in detail, a person's daily activity abilities with and without using ergonomic solutions (i.e. using alternate

movements and positions, activity simplification, pacing, planning, assistive devices, gadgets and equipment) or help. It includes numeric rating scales evaluating impact of conditions on e.g. pain, fatigue, mood and also 138 activities within 14 domains (sub-scales). This include: Eating /Drinking, In the Bathroom/ Personal Care, Getting Dressed/ Undressed, Bathing/ Showering, Cooking, Moving Around Indoors, Cleaning the House, Laundry / Clothes Care, Moving and Transfers, Communication, Moving Around Outside/ Shopping, Gardening/ Household Maintenance, Caring and Hobbies, Leisure and Social Activities. The EDAQ was originally developed and partially tested in the mid-1990's with women with rheumatoid arthritis in Sweden^{32,33} and translated into English by Beaton et al, 2000. It has been psychometrically tested several conditions including chronic pain³⁴.

PROMIS-29 v2.0 profile³⁰: The PROMIS-29 v2.0 profile measure assesses pain intensity using a single 0–10 numeric rating item and seven health domains (physical function, fatigue, pain interference, depressive symptoms, anxiety, ability to participate in social roles and activities, and sleep disturbance) using four items for each domain. PROMIS-29 has an excellent test-retest validity (≥ 0.80)²⁶

EQ-5D-5L³⁶: The descriptive system comprises five dimensions: mobility, self-care, usual activities, pain/discomfort and anxiety/depression. Each dimension has 5 levels: no problems, slight problems, moderate problems, severe problems and extreme problems. The patient is asked to indicate his/her health state by ticking the box next to the most appropriate statement in each of the five dimensions. This decision results in a 1-digit number that expresses the level selected for that dimension. The digits for the five dimensions can be combined into a 5-digit number that describes the patient's health state. The EQ VAS records the patient's self-rated health on a vertical visual analogue scale, where the endpoints are labelled 'The best health you can imagine' and 'The worst health you can imagine'. The VAS can be used as a quantitative measure of health outcome that reflect the patient's own judgement. EQ-5D-5L exhibits excellent psychometric properties across a broad range of populations, conditions and settings³⁷.

Furthermore, CRPS participants will undergo a clinical test to measure their tactile acuity, the two-point discrimination threshold (2PD³⁸), which will be assessed at the

pulp of the index finger or hallux (depending on the CRPS location, taking approximately 5 minutes) to all CRPS patients included.

Two point discrimination threshold at the pulp of the index finger or hallux: As a measure of tactile acuity, a two point discrimination test will be undertaken on the distal pulp of the index fingers (IF) of both the affected and unaffected hands (both IFs in HVs) according to Moberg's method (1990)³⁸. This test assesses the smallest distance at which an individual can clearly distinguish between two points applied simultaneously to the skin. With the participant's eyes closed, the aesthesiometer (Homecraft Rolyan, Nottingham, UK) is applied to the surface with the smallest possible distance between the two points until the skin blanches. The participant reports whether they feel the touch of one or two points. The distance between the two points is gradually increased for each trial until the participant correctly discerns two rather than one point. Three consecutive correct answers at the smallest discernable distance determine the two-point discrimination threshold (2ptDT). We will perform three 2ptDT assessments over the course of the intervention (i.e. at baseline, half way through the intervention, and immediately after the intervention). Sham trials involving stimulation of one point only will be pseudo-randomly included, with a total of 1-4 sham trials per 2ptDT assessment. Three threshold measurement trials will be taken on the index finger of each hand during each 2ptDT assessment. The mean of these trials will be calculated for each IF. The estimated completion time for each 2ptDT assessment is 5 minutes. Patients' two-point discrimination will be assessed using this tool twice in total – once at the beginning of session 2 and once at the end of session 3.

- *Training for treatment partner:* in addition to the outcome measures, [name] will individually clinically assess each CRPS patient participant including but not limited to:
 - Pain assessment: Pain intensity, pain location, pain triggers, pain beliefs/attitudes, presence of sensory symptoms (such as allodynia and/or hypersensitivity).
 - Posture (standing / sitting, postural shift).

- Functional strategies (including posture, transfers and ADLs): Inability/struggle to perform certain tasks involving the painful limb (e.g. gait or reach-to-grasp).
- Current mobility / falls history / risk of falls.
- Movement (range, strength, quality, weakness, motor dysfunction).
- Significant Dysfunction (e.g. BPD, allodynia, hypersensitivity, dystonia, hypervigilance, inattention, relationship with affected body part (e.g. attention, feelings, associations, perception, representation, amputation desire)
- Secondary Issues (e.g. non-CRPS symptoms, incontinence).

Based on each clinical presentation, [name] will produce an individualized CMR treatment for each CRPS participant: This treatment plan will consist on 2-5 CMR tasks that the treatment partner will deliver to CRPS participant during the intervention phase. A hard copy of every task will be handed to the treatment partner (an example can be found in the Appendix section 1). For every single CMR tasks the follow information will be given:

- Task number.
- Task name.
- Task description.
- Material required (e.g. different fabrics).
- Patient position.
- Modality includes a step-by-step procedure to deliver the task.
- Number of repetitions:
- Photos:

As a part of session 1, treatment partner will observe and learn the treatment plan under the supervision of [name] (i.e. practising the exercises with [name]'s guidance). The training session will end when treatment partner will be competent enough to deliver the intervention to good quality standards (will be assessed using the CMR tasks structure; cognitive problem (treatment partner is able to ask the question that

prompts the sensory discrimination - perceptual hypothesis (the CRPS participants is aware of which sensory information they have to focus on (e.g. tactile or proprioception) and verification (the treatment partner prompts the CRPS participants to check if they answer correctly). In case the treatment partner does not gain enough competency to deliver the intervention, further training will be offered from the lead investigator. A short questionnaire will be used to assess understanding and competency regarding the study intervention. Treatment partner will receive a hard copy with written guidance of the CMR tasks to be delivered including delivery instructions (an example can be found in the Appendix section 1).

There will be opportunities for both the CRPS patient and treatment partner to ask questions regarding CMR. The overall goal of this session is to prepare both CRPS patients and treatments partner to engage with the CMR treatment.

The anticipated total duration of session 2 is up to 3 hours with a rest break within the session.

Intervention phase:

The CMR home-intervention involves the recommended treatment plan being delivered by the treatment partner over a four-week period. The CRPS patient and treatment partner can refer to the written guidance provided for the different recommended tasks (an example can be found in the Appendix section 1). As part of a feasibility study the CRPS-patient and treatment partner would have agreed with [name] about the duration and frequency of the intervention sessions and this will be recorded in the written treatment plan. [name] will encourage treatment partner to deliver the intervention daily. A rehabilitation diary will be provided to record frequency and duration of treatment sessions and any other comments (see Appendix 2 for an example).

Weekly Zoom meetings will be agreed between the CRPS-participant, treatment partner, [name] and [name] (Cognitive Multisensory Rehabilitation Centre, Italy) in order to evaluate progress on the intervention and modify treatment plan if required (e.g. increasing the complexity of the tasks or adding new CMR tasks). [name] who will supervise the CMR treatment during the weekly zoom calls, providing further specialist CMR knowledge.

Session 2: Post-intervention clinical assessments

Following the four-week home-delivered intervention, CRPS patients and treatment partner will be invited to undergo the post-intervention clinical assessment session at the RUH in Bath. Post-intervention clinical assessments includes a repeat data collection of the self-reported measures completed at session 1 (see section Session 1).

Furthermore, CRPS-patients and treatment partner will be invited to attend an interview by [name] in order to gain insight in their experience of delivering/receiving CMR. The interview questions will be devised in order to gain insights on adherence, efficiency, acceptability, and safety of the intervention. This interview will include the discussion of:

- Content,
- Goals,
- Duration,
- Frequency and
- Modality of delivery of CMR

The anticipated total duration of session 1 is up to 1 hour.

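### Lower-limb CRPS is eligible and the hallux is a named test site, but the two-point discrimination steps are written only for index fingers and the body perception drawing only for upper limbs

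*Protocol*

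**What the plan says.** The inclusion criteria require Type I CRPS in one limb and do not restrict it to the arm. Under the training heading in section 3.3, the clinical assessment lists "Inability/struggle to perform certain tasks involving the painful limb (e.g. gait or reach-to-grasp", so patients with a painful leg or foot are evidently expected.

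For tactile acuity, the lead sentence in section 3.3 places the 2PD test at the "pulp of the index finger or hallux (depending on the CRPS location", for all CRPS patients, and the sub-heading also names the hallux. The procedure under that sub-heading then gives:

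- Site: "a two point discrimination test will be undertaken on the distal pulp of the index fingers (IF) of both the affected and unaffected hands".
- Trials: "Three threshold measurement trials will be taken on the index finger of each hand during each 2ptDT assessment".
- Averaging: "The mean of these trials will be calculated for each IF".

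For the Bath body perception disturbance scale, the drawing item is introduced in general terms: "The final item involves an illustration of the mental representation of both the affected and unaffected limb". The instruction that follows is that "the participant generates a mental picture of both upper limbs commencing with their unaffected side".

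Section 3.4 inspects each person's change on each outcome measure against clinically meaningful differences. Section 4.2 includes tactile acuity and body perception disturbances among five anticipated benefits.

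**The concern.** The operating steps for two outcome measures conflict with the protocol's own eligibility rule and, for 2PD, with its own lead sentence and sub-heading. For a patient with CRPS in a foot, the reference to an affected hand points to nothing. An assessor who works from the detailed steps would test two fingers that are not the affected site. An assessor who follows the drawing instruction would record two arms.

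2PD is the only tactile acuity test in the protocol, and section 3.4 reads changes patient by patient. For a lower-limb patient, the text leaves open whether a 2PD change refers to the affected foot or to the fingers. The drawing score, obtained as instructed, would not depict the affected limb but would still enter the seven-item total. Because the study is meant to inform larger ones, an ambiguous measurement procedure could be carried forward.

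**Working it through.** There is no stated figure to reproduce, because this is a question of measurement specification. The check compares the passages and then bounds the effect.

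**2PD: which steps name a site**

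| Element (section 3.3) | Site given |
|---|---|
| Lead sentence | Index finger or hallux, by CRPS location |
| Sub-heading | Index finger or hallux |
| Where the test is applied | Index fingers of both hands |
| Where the three trials are taken | Index finger of each hand |
| What is averaged | Each index finger |
| Pressure to blanching, widening distance, three correct answers, sham trials | Site-neutral |

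The three procedural steps that name a site all name only the index finger. The site-neutral steps apply to the hallux as they stand. No sentence in the procedure itself mentions the hallux, toe or foot.

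**2PD: extent if the detailed steps are followed in a lower-limb patient**

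- Per assessment: 3 trials × 2 sides = 6 threshold trials, all at the fingers.
- Per patient: 6 × 2 = 12 over two assessments, or 6 × 3 = 18 over three. The protocol states both counts; that is a separate inconsistency.

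**Drawing: weight in the total score**

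- "Five of these seven items are rated on a 0 to 10 scale": 5 × 10 = 50 points.
- The drawing is graded 0, 1 or 2: at most 2 points.
- Points with a stated range: 50 + 2 = 52.
- Share of the drawing: 2 / 52 = 3.8%. This is an upper bound, because the range of the sixth item (size, weight, pressure and temperature) is not given and would add to the denominator.

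**Number of patients affected**

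Five CRPS patients are planned and the split by limb is not stated, so between 0 and 5 could have lower-limb CRPS. Each one is 1/5 = 20% of the sample for the per-person changes in section 3.4.

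**The case against.** The best answer is that the site rule for 2PD is already fixed, in both the lead sentence and the sub-heading. On that reading the text below simply works through the finger case, and its pattern of two sides, three trials and a mean per side carries over to the hallux. A sensible assessor would not test the fingers of a patient with foot CRPS under a heading that names the hallux. One researcher does both the baseline and the post-intervention assessments (Table 1), so a change of site between visits is unlikely. For the drawing, the surrounding text speaks of the affected limb throughout, so the restriction to upper limbs can be read as a stray word. Finally, the aims are suitability and feasibility, no primary outcome is named, and outcome changes serve only as preliminary insight.

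Much of this stands, and it limits the weight of the point. The 2PD error arises only if the detailed steps are preferred to the lead sentence, most of the stimulus procedure is unaffected, the drawing effect is small, and no feasibility conclusion depends on either measure. It does not remove the contradiction. Even an assessor who goes to the hallux is not told in terms whether both sides are tested there, how many trials are taken, or what is averaged. For the drawing, no alternative instruction is given for a lower limb. The procedure also refers to index fingers in an abbreviated group, HVs, that the protocol neither defines nor recruits. This suggests, as an inference, that the text was carried over from another study and that the restriction was not intended.

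**Conclusion.** The concern holds as a modest but real contradiction within section 3.3. Read literally, the 2PD site, trial and averaging steps and the drawing instruction do not cover the affected limb of an eligible lower-limb patient.

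For 2PD, the consequence depends on which sentence the assessor follows; if it is the detailed steps, every threshold trial in that patient is at the wrong site. For the drawing, the consequence follows from the instruction as written but touches less than 4% of the total score. Both statements assume that at least one lower-limb patient is enrolled, which the eligibility rule allows but the protocol does not quantify. Test site and instrument administration are protocol content, so this is not a matter left to a statistical analysis plan. It should be corrected, but it does not threaten the study's feasibility aims.

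**What to change.** Reconcile the passages in section 3.3.

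- **2PD.** State, for example: *tested at the index finger pulps for upper-limb CRPS and at the hallux pulps for lower-limb CRPS, on the affected and unaffected sides; three threshold trials per side at each assessment; mean calculated for each side.* Remove the reference to the undefined HVs group.
- **Drawing.** Replace the reference to upper limbs with *the affected limb and its opposite counterpart*.

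If only upper-limb patients are in fact intended, the inclusion criteria and the hallux wording should say so instead.

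The cost is protocol wording only. The hallux is already a named site and both sides are already tested, so no testing or visit time is added.
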